### 1.4.1.1. Details of Important Adverse Drug Reactions

#### 1.4.1.1.1. Liver Enzyme Elevations

Treatment with laquinimod has been associated with mostly mild, asymptomatic, and reversible liver enzyme elevations (Table 4) that generally occurred within 6 months after initiation of treatment.

In clinical trials, laquinimod was discontinued if elevation of liver enzymes exceeded 5 times the upper limit of the normal range (ULN) for more than 2 weeks in the absence of a clear alternative explanation; if the elevation exceeded 8 times the ULN, laquinimod was discontinued without further delay.

**Table 4: ALLEGRO and BRAVO: Shift from Normal Test at Baseline to Highest Value for Alanine Aminotransferase, Aspartate Aminotransferase, and Gamma-Glutamyl Transpeptidase Tests**

Test	Range of Increase	Placebo	Laquinimod 0.6 mg
AST (IU/L)		Patients with Normal Test at Baseline: N = 977	Patients with Normal Test at Baseline: N = 950
	> 1 and $\leq$ 3 x ULN	83 (8.5%)	159 (16.7%)
	> 3 and $\leq$ 5 x ULN	6 (0.6%)	9 (0.9%)
	> 5 and $\leq$ 8 x ULN	4 (0.4%)	1 (0.1%)
	> 8 x ULN	2 (0.2%)	0 (0.0%)
ALT (IU/L)		Patients with Normal Test at Baseline: N = 930	Patients with Normal Test at Baseline: N = 888
	> 1 and $\leq$ 3 x ULN	165 (17.7%)	262 (29.5%)
	> 3 and $\leq$ 5 x ULN	5 (0.5%)	30 (3.4%)
	> 5 and $\leq$ 8 x ULN	6 (0.6%)	5 (0.6%)
	> 8 x ULN	7 (0.8%)	5 (0.6%)
GGT (IU/L)		Patients with Normal Test at Baseline: N = 930	Patients with Normal Test at Baseline: N = 906
	> 1 and $\leq$ 3 x ULN	90 (9.7%)	147 (16.2%)
	> 3 and $\leq$ 5 x ULN	11 (1.2%)	22 (2.4%)
	> 5 and $\leq$ 8 x ULN	1 (0.1%)	6 (0.7%)

The percentages listed in the table refer to all patients with normal values at baseline.

ULN = Upper limit of normal range; AST = aspartate aminotransferase; ALT = alanine aminotransferase; GGT = gamma-glutamyl transpeptidase; IU/L = international units/L

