#### **7.3.1. Serum Chemistry**

The following serum chemistry tests will be performed at all study visits (except where stated):

- electrolytes
- fibrinogen
- glucose
- urea
- creatinine (Note: GFR will be estimated at all visits)
- ALT
- AST
- GGT
- alkaline phosphatase
- CPK

- in case of CPK results >ULN, creatine kinase MB isoenzyme (CK-MB) and troponin will be tested by the central laboratory.
- in case of CPK >10×ULN, an unscheduled visit to assess urine myoglobin will be required. The following blood tests will be repeated at the unscheduled visit: CPK, blood urea nitrogen, creatinine, electrolytes including potassium, calcium, phosphate.
- CRP
- pancreatic amylase
  - lipase will be tested in case of abnormal pancreatic amylase results
- total protein
- albumin
- direct and total bilirubin
- fasting lipid profile at weeks 0 and 48 and every 48 weeks until completion/ET.
- TSH, T3, and T4 at weeks 0 and 24 and every 24 weeks until completion/ET.
- Coagulation profile (prothrombin time [PT], activated partial thromboplastin time [aPTT] and INR), to be tested only if required according to Guidance on Safety Monitoring (see [Appendix B](#)).

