## APPENDIX B. GUIDANCE ON SAFETY MONITORING

### 1. Guidance on Monitoring Patients with Elevated Liver Function Tests

Liver enzymes (ALT, AST, GGT, ALP), as well as direct and total bilirubin will be measured at each study visit.

In any case of elevated ALT or AST to a level exceeding of  $\geq 2 \times$ ULN (including patients whose baseline ALT or AST levels are  $\geq 2 \times$  and  $\leq 3 \times$  the ULN, who may be enrolled in the study), a thorough medical history and physical examination with a focus on liver disease should be undertakena. In addition, the patient should be instructed to refrain from alcoholic beverages.

In case of symptoms compatible with drug-induced liver injury, the patient should be invited for an unscheduled visit to measure liver enzymes as soon as possible.

Solitary elevations of total bilirubin, not accompanied by elevations of ALT or AST should be managed according to the discretion of the Treating Neurologist.

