8.5. Clinical Laboratory Test

All laboratory tests will be presented in SI units. By-visit summaries for chemistry and hematology laboratory tests including actual values and changes from baseline to each visit will be summarized using descriptive statistics. Shifts (below, within, and above the normal range) from baseline to each visit will be summarized using descriptive statistics. In order to calculate the percentages for the shifts summary, the total number of patients with available laboratory test results at baseline and at the post baseline visit will be used as the denominator for each relevant laboratory test and time point.

The incidence of abnormal values (below or above normal range) and the incidence of potentially clinically significant abnormal values (PCSA) (according to criteria specified in [Table 3](#)) will be summarized for laboratory data using descriptive statistics. The denominator for calculating the percentage of patients with at least 1 abnormality/PCSA for the group of chemistry/hematology tests will be the number of patients with both baseline and post baseline

laboratory result for at least 1 of the chemistry/hematology tests in that group. The denominator for calculating the percentage of patients with at least 1 abnormality/PCSA for each separate test will be the number of patients with both baseline and post baseline result for that test.

In addition, shift analysis from baseline to any time during the study for abnormal values as well as for PCSA values will be summarized using descriptive statistics. The shift categories for abnormal values will be presented as following: from below/within normal range at baseline to above normal range during the study, from above/within normal range at baseline to below normal range during the study, and condition not changed/changed to normal range value. The shift categories for PCSA values will be presented as following: from low/non PCSA value at baseline to high PCSA value during the study, from high/ non PCSA value at baseline to low PCSA value during the study, and condition not changed/changed to non PCSA value. In addition shift analysis for PCSA will also be presented as shift from normal baseline values to PCSA any time during the study following baseline. The denominator for calculating the percentages of patients will be the number of patients with both baseline and post baseline measurements for a specific test.

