Table 3: Criteria for Potentially Clinically Significant Laboratory Values

Test	Criterion value
Serum chemistry	
Sodium	≤ 130 mmol/L ≥ 150 mmol/L
Potassium	≤ 3.2 mmol/L ≥ 5.5 mmol/L
Calcium	≤ 1.87 mmol/L ≥ 2.75 mmol/L
Phosphate	≤ 0.65 mmol/L ≥ 1.61 mmol/L
Glucose	≤ 3 mmol/L ≥ 13.88 mmol/L
Blood Urea Nitrogen	≥ 11.16 mmol/L
Alanine aminotransferase (ALT)	≥ 3 x ULN
Aspartate aminotransferase (AST)	≥ 3 x ULN
Alkaline phosphatase	≥ 3 x ULN
Gammaglutamyl Transpeptidase (GGT)	≥ 3 x ULN
Creatine phosphokinase (CPK)	≥ 3 x ULN
Creatinine	≥ 177 μ mol/L
Bilirubin (total)	≥ 28 μ mol/L
Albumin	≤ 25 g/L

Table 3: Criteria for Potentially Clinically Significant Laboratory Values (Continued)

Test	Criterion value
C Reactive Protein	$\geq 3x$ ULN
Amylase, Pancreatic	$\geq 3x$ ULN
Hematology	
Hemoglobin Men	≤ 11.5 g/dL ≥ 20 g/dL
Women	≤ 10 g/dL ≥ 18.5 g/dL
Leukocytes	$\leq 2.5 \times 10^9/L$ $\geq 21 \times 10^9/L$
Neutrophils	$\leq 1.49 \times 10^9/L$
Platelets	$\leq 100 \times 10^9/L$ $\geq 600 \times 10^9/L$
Fibrinogen	$\geq 1.5x$ ULN

ULN=upper limit of normal range.

Boxplots for all hematology tests, Fibrinogen, CRP and P-Amylase will be presented over time, including baseline, and all scheduled visits. Data recorded during unscheduled visits will not be included in the box plots.

In addition, for patients with a confirmed hemoglobin decrease of more than 1 g/dL who completed at least one of the tests in the anemia panel following baseline visit, data from the anemia panel/B12 tests and change from baseline will be presented using descriptive statistics.

Moreover, shift analysis of Common Terminology Criteria for Adverse Events (CTCAE) grade from baseline to any time during the study for Hemoglobin test will be presented using descriptive statistics. Grades of CTCAE will be defined according to CTCAE, v4 and are presented in [Table 4](#). For the cases with normal hemoglobin value, the CTCAE grade will be assigned zero. The denominator for calculating the percentages of patients will be the number of patients with both baseline and post baseline Hemoglobin measurements.

Table 4: Common Terminology Criteria for Adverse Events for Hemoglobin, v4

Grade	Description
1	LLN - 10.0
2	10.0 - 8.0 g/dL
3	<8.0 g/dL
4	Life-threatening consequences; urgent intervention indicated
5	Death

Also, a graph for the evaluation of drug-induced serious hepatotoxicity (eDISH) will be presented. The following steps should be performed in order to construct this graph:

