1. For each patient in the ST population, find maximal post baseline value for ALT. If the same maximal value occurs in two separate visits, then the earlier visit value should be taken into account. Following that find the maximal Bilirubin(Total) value occurring after (or same day) the maximum ALT measurement occurred.
2. The maximal values identified in step 1 then should be divided by the ULN for each test accordingly.
3. Values received in step 2 will be presented in the scatter plot with ALT values on the x-axis and Bilirubin values on the y-axis. Two reference lines indicating extreme limits of 3 X ULN for ALT and 2 X ULN for Bilirubin will be shown as well.

Maximal values of AST, ALT and GGT at any time after randomization in terms of the upper normal range multiples will be provided in a separate table for patients with normal AST, ALT and GGT at baseline using descriptive statistics. The following intervals for maximal values will be used for this table: <= 1xULN, > 1xULN and <= 3xULN, > 3xULN and <= 5xULN, > 5xULN and <= 8xULN, > 8xULN. The denominator for calculating percentages will be the number of patients with post baseline hematology tests.

All analyses presented in the section will be repeated to include both part A and part B when the study is completed.

Listings for clinically significant abnormal laboratory data will be presented.

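### SAP 8.5 sets the wrong denominator for the liver-enzyme maxima table (15.108): it names the hematology panel and omits the normal-baseline condition

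*SAP*

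**What the plan says.** SAP 8.5 (Clinical Laboratory Test) describes a display of the maximum AST, ALT and GGT in multiples of the upper limit of normal (ULN), in five bands from at most 1×ULN to above 8×ULN. Its population is set first: the results "will be provided in a separate table for patients with normal AST, ALT and GGT at baseline using descriptive statistics". The paragraph closes with the denominator: "The denominator for calculating percentages will be the number of patients with post baseline hematology tests".

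Four other places bear on this:

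- SAP Table 3, in the same section, lists ALT, AST and GGT under serum chemistry, not hematology.
- Elsewhere in SAP 8.5 the shift displays use a test-specific denominator, "the number of patients with both baseline and post baseline measurements for a specific test".
- SAP 13.1 lists the table as 15.108.1 (Part A) and 15.108.2 (Part B) for the Safety Population. The title does not mention normal baselines, whereas the titles of 15.104 and 15.105 do.
- Protocol 1.4.1.1.1, Table 4, is the same kind of table for the two pivotal studies. Its footnote reads: "The percentages listed in the table refer to all patients with normal values at baseline".

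**The concern.** The people who can be counted in a band and the people in the denominator are defined by different rules. A patient whose ALT was raised at baseline cannot appear in any band, yet under the literal rule is still divided by, provided that a hematology result exists.

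Such patients can be enrolled. Protocol 4.2 excludes ALT or AST only from 3×ULN upward at screening and sets no GGT limit. Protocol Appendix B, section 1, provides for patients already at 2 to 3×ULN, "including patients whose baseline ALT or AST levels are" in that range.

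Liver enzyme elevation is a listed common reaction to the drug (protocol Table 3) and has its own stopping rules (protocol 3.6.2). The table that quantifies it should have a denominator that two programmers would compute in the same way, and that can be set beside protocol Table 4. A second ambiguity is attached: the SAP does not say whether normal at baseline is judged test by test or requires all three enzymes to be normal together.

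**Working it through.** The SAP gives no percentage for this table, and this trial's baseline enzyme counts are not in the documents. The check therefore uses protocol Table 4.

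**Step 1. Which denominator reproduces Table 4?** Percentage = count / patients normal on that test at baseline. For laquinimod 0.6 mg, ALT above 1 and up to 3×ULN: 262/888 = 29.5%, as printed. All 22 percentages in Table 4 reproduce to rounding with the per-test normal-baseline N. Dividing by all 983 treated patients does not reproduce the printed ALT figure: 262/983 = 26.7%.

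**Step 2. What does the literal rule do?** Inputs: normal at baseline on 0.6 mg, AST 950, GGT 906, ALT 888 (protocol Table 4); all pivotal 0.6 mg patients, 983 (protocol 1.4.1). Assumption: all 983 had a post-baseline hematology result. Relative understatement = 1 − (normal at baseline / all tested).

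| Test | Normal / all | Relative understatement | Above 3×ULN, normal-baseline denominator | Above 3×ULN, all patients |
|---|---|---|---|---|
| AST | 950/983 = 96.6% | 3.4% | 10/950 = 1.05% | 10/983 = 1.02% |
| GGT | 906/983 = 92.2% | 7.8% | 28/906 = 3.09% | 28/983 = 2.85% |
| ALT | 888/983 = 90.3% | 9.7% | 40/888 = 4.50% | 40/983 = 4.07% |

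For ALT above ULN in any band, 302/888 = 34.0% becomes 302/983 = 30.7%. Together, the ALT bands (including at most 1×ULN) would sum to 888/983 = 90.3% instead of 100%.

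**Step 3. If all three tests must be normal together.** The joint count is not given but is bounded. It is at most the smallest single count, 888, and at least 950 + 906 + 888 − 2 × 983 = 778. The understatement is then between 1 − 888/983 = 9.7% and 1 − 778/983 = 20.9%.

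**Step 4. If the denominator is confined to the table's own patients.** Only the panel name is then wrong. Protocol 7.3.1 and 7.3.2 schedule serum chemistry and the blood count at all study visits, so nearly the same patients have both. The effect is close to zero, and its direction is not fixed.

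**The case against.** The strongest reply is that the closing sentence belongs to a paragraph that has already limited the table to normal baselines, and that it nowhere says all patients. It can be read as the patients in this table who have post-baseline data. SAP 8.5 writes another denominator in the same way: the shift from normal baseline to potentially clinically significant values also has a rule based only on data availability, without repeating the baseline condition. This stands. It means that understatement is a consequence of one reading, not a certainty.

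A reader might also infer that the dilution differs between arms, because 930/977 = 95.2% for placebo ALT would mean a loss of 4.8%, against 9.7% on laquinimod. The documents do not support this. The 977 is the number of placebo patients with normal AST, so it is only a lower bound on the placebo total, which is not given. A total of about 1030 would give 930/1030 = 90.3%, the same dilution as on laquinimod. With randomized arms, baseline abnormality is expected to balance, and the ratio between arms then barely moves.

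The size is also small. The illustrated ALT shift above 3×ULN is 4.50 − 4.07 = 0.43 percentage points. With the 140 patients per arm in SAP 3.3, one patient is 1/140 = 0.7 points. Other planned outputs cover the same signal: Tables 15.98, 15.102 and 15.104, and the plot for drug-induced hepatotoxicity. Counts are shown beside percentages, so a reader who knew the normal-baseline N could recompute the rate.

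None of this makes the sentence right. Hematology is the wrong panel on either reading, and nothing else in the SAP settles which patients are meant.

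**Conclusion.** The denominator for Table 15.108 is wrong as written: wrong panel, and no normal-baseline condition. If it is applied literally, the percentages are too low, the bands do not sum to 100%, and the results are not comparable with protocol Table 4. If it is read as limited to the table's own population, the numerical effect is near zero.

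The figures of 3.4% to 9.7% per test, and 9.7% to 20.9% under joint normality, are an illustration and not an estimate for this trial. They come from relapsing-remitting patients in the pivotal studies and assume that all 983 were tested. A reader might take them to show that this trial's liver rates are understated, or are understated more in one arm; the documents show neither.

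Severity is minor: the table is descriptive, no efficacy result or decision rule depends on it, and related safety outputs remain.

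**What to change.** Replace both the population sentence and the denominator sentence in SAP 8.5. Changing the denominator alone could leave jointly normal patients in the numerator over a per-test denominator. Suggested wording:

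> For each of AST, ALT and GGT separately, the table includes patients in the ST population with a normal baseline value of that test, and the denominator is the number of these patients with at least one post-baseline value of that test.

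This settles the choice between per-test and joint normality, makes the bands sum to 100%, and follows the per-test normal-baseline basis of protocol Table 4. Adding the normal-baseline restriction to the titles of 15.108.1 and 15.108.2 in SAP 13.1 would keep the list consistent.

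The cost is a small text edit and the matching table program, with no new data. Displayed percentages may become slightly less favourable than under the literal rule.

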8.6. Vital Signs

By-visit summaries for vital signs including actual values and changes from baseline to each visit will be summarized using descriptive statistics. The incidence of potentially clinically significant abnormal values will be summarized for selected vital signs using descriptive statistics.

[Table 5](#) specifies the criteria for identifying vital signs as potentially clinically significantly abnormal. Note that in order to be identified as potentially clinically significantly abnormal, a value would need to meet both conditions below, ie, have a value beyond the criterion value and a change of at least the magnitude specified in the change from baseline column.

Table 5: Criteria for Potentially Clinically Significant Vital Signs

Vital Sign	Criterion value	Change relative to baseline
Pulse	≥120 bpm	Increase of ≥30
	≤45 bpm	Decrease of ≥30
Systolic blood pressure	≥180 mm Hg	Increase of ≥30
	≤90 mm Hg	Decrease of ≥30
Diastolic blood pressure	≥100 mm Hg	Increase of ≥20
	≤50 mm Hg	Decrease of ≥20

All analyses presented in the section will be repeated to include both part A and part B when the study is completed.

A listing for potentially clinically significant abnormal vital signs will be presented.

8.7. **Electrocardiogram**

ECG findings at each week will be summarized using descriptive statistics for investigator's interpretations (normal, abnormal not clinically significant, abnormal clinically significant, missing) and for ERT interpretation (normal, abnormal, unable to evaluate). Shifts from baseline to each visit will be summarized using descriptive statistics.

Summary statistics for electrocardiogram variables evaluated by ERT (Heart Rate, PR Interval, QRS Interval, QT Interval, QTc Interval Bazett, QTc Interval Fridericia, RR Interval) will be presented at baseline, and each visit. Actual values and changes from baseline to each visit will be summarized using descriptive statistics.

Categorical analysis of QTc Intervals (Bazett and Fridericia), according to International Conference on Harmonisation (ICH) guideline: E14 – "The Clinical Evaluation of QT/QTc Interval Prolongation and Proarrhythmic Potential for Non-Antiarrhythmic Drugs", will be presented. Incidence of subjects within each category at baseline will be presented for each parameter. Shift analysis from baseline to each scheduled visit and to any time during study will be performed for each parameter.

All analyses presented in the section will be repeated to include both part A and part B when the study is completed.

The cut off points for categorical analysis of QTc Interval (msec) (Bazett and Fridericia) are defined in [Table 6](#).

Table 6: Cut off Points for Categorical Analysis of QTc Interval (msec) (Bazett and Fridericia)

QTc Interval (msec)	<=450
QTc Interval (msec)	>450 and <=480
QTc Interval (msec)	>480 and <=500
QTc Interval (msec)	>500
QTc Interval (msec) Increase from Baseline	<=30
QTc Interval (msec) Increase from Baseline	>30 and <=60
QTc Interval (msec) Increase from Baseline	>60

8.8. **Concomitant Medications**

All concomitant medications will be coded using the WHO Drug. The incidence of concomitant medications will be summarized using descriptive statistics by therapeutic class and preferred term. Patients are counted only once in each therapeutic class category, and only once in each preferred term category. Concomitant medications will include all medications taken while a patient participated in the study.

When the study is completed, the table of concomitant medications will be generated again to include both part A and part B.

9. PHARMACOKINETIC ANALYSIS

A single blood sample will be collected from all patients at weeks 4, 8, 12, 24 and 48. Pharmacokinetics of laquinimod will be evaluated using a PPK approach. The effect of covariates on the pharmacokinetics of laquinimod will be evaluated. Possible covariates will include demographic variables (eg, age, gender, body weight and ethnicity), clinical variables, concomitant medications, blood and urine chemistry variables and markers of renal function (creatinine clearance and serum creatinine).

This analysis will be reported in a separate PPK report.

10. ANALYSIS OF ADDITIONAL EXPLORATORY PARAMETERS

The analysis of the following variable will be specified in separate documents:

- PGx measures
- Potential biomarker measures
- Ancillary studies measures

11. STATISTICAL SOFTWARE

All data listings, summaries, and statistical analyses will be generated using SAS®.

12. CHANGES TO PROTOCOL SPECIFIED ANALYSES

The following changes to protocol specified analyses are introduced in this SAP:

- Multiplicity adjustment at alpha level of 5% was added for the analyses of the primary and secondary endpoints.
- Sensitivity analyses for primary and secondary endpoints which use data recorded after patient early terminates treatment and continues to come to the follow up visits were removed.

13. LIST OF SUMMARIES AND LISTINGS

13.1. Summary Tables

Summary number	Title	Population	Data Lock
15.1.1	Patient Disposition by Treatment Group	All Patients	Part A
15.1.2	Patient Disposition by Treatment Group	All Patients	Part B
15.2	Distribution of Patients by Country and Treatment Group	ITT Population	Part A
15.3	Distribution of Patients by Country, Site, and Treatment Group	ITT Population	Part A
15.4.1	Demographics by Treatment Group	ITT Population	Part A
15.4.2	Demographics by Treatment Group	mITT1 Population	Part A
15.4.3	Demographics by Treatment Group	Patients who ET in Part A	Part A
15.4.4	Demographics by Treatment Group	Patients who Completed Part A	Part A
15.4.5	Demographics by Treatment Group	Patients who ET in Part B	Part B
15.4.6	Demographics by Treatment Group	Patients who Completed Part B	Part B
15.5.1	PPMS Characteristics by Treatment Group	ITT Population	Part A
15.5.2	PPMS Characteristics by Treatment Group	mITT1 Population	Part A
15.5.3	PPMS Characteristics by Treatment Group	Patients who ET in Part A	Part A
15.5.4	PPMS Characteristics by Treatment Group	Patients who Completed Part A	Part A
15.5.5	PPMS Characteristics by Treatment Group	Patients who ET in Part B	Part B
15.5.6	PPMS Characteristics by Treatment Group	Patients who Completed Part B	Part B
15.6.1	Baseline MRI Measurements by Treatment Group	ITT Population	Part A
15.6.2	Baseline MRI Measurements by Treatment Group	mITT1 Population	Part A
15.6.3	Baseline MRI Measurements by Treatment Group	Patients who ET in Part A	Part A
15.6.4	Baseline MRI Measurements by Treatment Group	Patients who Completed Part A	Part A
15.6.5	Baseline MRI Measurements by Treatment Group	Patients who ET in Part B	Part B
15.6.6	Baseline MRI Measurements by Treatment Group	Patients who Completed Part B	Part B
15.7.1	Tobacco Usage by Treatment Group	ITT Population	Part A
15.7.2	Tobacco Usage by Treatment Group	mITT1 Population	Part A
15.7.3	Tobacco Usage by Treatment Group	Patients who ET in Part A	Part A
15.7.4	Tobacco Usage by Treatment Group	Patients who Completed Part A	Part A

Summary number	Title	Population	Data Lock
15.7.5	Tobacco Usage by Treatment Group	Patients who ET in Part B	Part B
15.7.6	Tobacco Usage by Treatment Group	Patients who Completed Part B	Part B
15.8	Abnormal Medical History Findings by System Organ Class, Preferred Term and Treatment Group	ITT Population	Part A
15.9	Prior Medications by Therapeutic Class, Preferred Term, and Treatment Group	ITT Population	Part A
15.10	MS Disease Modifying Treatment History by Therapeutic Class, Preferred Term, and Treatment Group	ITT Population	Part A
15.11	Electrocardiogram Findings at Baseline Based on Investigator Interpretation by Treatment Group	ITT Population	Part A
15.12	Electrocardiogram Findings at Baseline Based on ERT Interpretation by Treatment Group	ITT Population	Part A
15.13.1	Protocol Violations by Treatment Group	ITT Population	Part A
15.13.2	Protocol Violations by Treatment Group	ITT Population	Part B
15.14	Major Protocol Violations by Treatment Group	ITT Population	Part A
15.15	Primary Analysis: Percentage Brain Volume Change (PBVC) from Baseline to Week 48	mITT1 Population	Part A
15.16	Primary Analysis Treatment by Covariate Interaction Evaluation: Percentage Brain Volume Change (PBVC) from Baseline to Week 48	mITT1 Population	Part A
15.17	Descriptive Statistics for Percentage Brain Volume Change (PBVC) by Visit and Treatment Group	mITT1 Population	Part A
15.18	Sensitivity Analysis for Primary Endpoint: Percentage Brain Volume Change (PBVC) from Baseline to Week 48	PP Population	Part A
15.19	Descriptive Statistics for Percentage Brain Volume Change (PBVC) by Visit and Treatment Group	PP Population	Part A
15.20	Sensitivity Analysis for Primary Endpoint: Percentage Brain Volume Change (PBVC) from Baseline to Week 48 – Unadjusted for Covariates	mITT1 Population	Part A
15.21	Sensitivity Analysis for Primary Endpoint: Percentage Brain Volume Change (PBVC) from Baseline to Week 48 – Adjusted for Additional Covariates	mITT1 Population	Part A
15.22.1	Secondary Analysis: Time to 12 Weeks Confirmed Disability Progression as Measured by EDSS	ITT Population	Part A
15.22.2	Exploratory Analysis: Time to 12 Weeks Confirmed Disability Progression as Measured by EDSS	ITT Population	Part B
15.23.1	Secondary Analysis Proportional Hazards Assumption Evaluation: Time to 12 Weeks Confirmed Disability Progression as Measured by EDSS	ITT Population	Part A

Summary number	Title	Population	Data Lock
15.23.2	Exploratory Analysis Proportional Hazards Assumption Evaluation: Time to 12 Weeks Confirmed Disability Progression as Measured by EDSS	ITT Population	Part B
15.24.1	Distribution of 12 Weeks Confirmed Disability Progression as Measured by the EDSS by Treatment Group	ITT Population	Part A
15.24.2	Distribution of 12 Weeks Confirmed Disability Progression as Measured by the EDSS by Treatment Group	ITT Population	Part B
15.25.1	Descriptive Statistics for EDSS Score and Change From Baseline to Each Visit by Treatment Group	ITT Population	Part A
15.25.2	Descriptive Statistics for EDSS Score and Change From Baseline to Each Visit by Treatment Group	ITT Population	Part B
15.26.1	Secondary Analysis: Time to 12 Weeks Confirmed Disability Progression as Measured by EDSS or T25FW	ITT Population	Part A
15.26.2	Exploratory Analysis: Time to 12 Weeks Confirmed Disability Progression as Measured by EDSS or T25FW	ITT Population	Part B
15.27.1	Secondary Analysis Proportional Hazards Assumption Evaluation: Time to 12 Weeks Confirmed Disability Progression as Measured by EDSS or T25FW	ITT Population	Part A
15.27.2	Exploratory Analysis Proportional Hazards Assumption Evaluation: Time to 12 Weeks Confirmed Disability Progression as Measured by EDSS or T25FW	ITT Population	Part B
15.28.1	Distribution of 12 Weeks Confirmed Disability Progression as Measured by EDSS or T25FW by Treatment Group	ITT Population	Part A
15.28.2	Distribution of 12 Weeks Confirmed Disability Progression as Measured by EDSS or T25FW by Treatment Group	ITT Population	Part B
15.29.1	Secondary Analysis: Timed 25-Foot Walk Score Change From Baseline to Week 48	mITT2 Population	Part A
15.29.2	Exploratory Analysis: Timed 25-Foot Walk Score Change From Baseline to Each Visit	mITT2 Population	Part B
15.30.1	Descriptive Statistics for Timed 25-Foot Walk Score and Change From Baseline to Each Visit by Treatment Group	mITT2 Population	Part A
15.30.2	Descriptive Statistics for Timed 25-Foot Walk Score and Change From Baseline to Each Visit by Treatment Group	mITT2 Population	Part B
15.31	Secondary Analysis: Number of New T2 Lesions at Week 48	mITT1 Population	Part A
15.32	Descriptive Statistics for the Number of New T2 Lesions at Week 48 by Treatment Group	mITT1 Population	Part A
15.33.1	Exploratory Analysis: CVLT-II Score Change From Baseline to Week 48	mITT2 Population	Part A
15.33.2	Exploratory Analysis: CVLT-II Score Change From Baseline to Each Visit	mITT2 Population	Part B

Summary number	Title	Population	Data Lock
15.34.1	Descriptive Statistics for CVLT-II Score and Change From Baseline to Each Visit by Treatment Group	mITT2 Population	Part A
15.34.2	Descriptive Statistics for CVLT-II Score and Change From Baseline to Each Visit by Treatment Group	mITT2 Population	Part B
15.35.1	Exploratory Analysis: BVMT-R Score Change From Baseline to Week 48	mITT2 Population	Part A
15.35.2	Exploratory Analysis: BVMT-R Score Change From Baseline to Each Visit	mITT2 Population	Part B
15.36.1	Descriptive Statistics for BVMT-R Score and Change From Baseline to Each Visit by Treatment Group	mITT2 Population	Part A
15.36.2	Descriptive Statistics for BVMT-R Score and Change From Baseline to Each Visit by Treatment Group	mITT2 Population	Part B
15.37.1	Exploratory Analysis: Time to 12 Weeks Confirmed Disability Progression as Measured by at least 1 of 4 Types of Events	ITT Population	Part A
15.37.2	Exploratory Analysis: Time to 12 Weeks Confirmed Disability Progression as Measured by at least 1 of 4 Types of Events	ITT Population	Part B
15.38.1	Exploratory Analysis Proportional Hazards Assumption Evaluation: Time to 12 Weeks Confirmed Disability Progression as Measured by at least 1 of 4 Types of Events	ITT Population	Part A
15.38.2	Exploratory Analysis Proportional Hazards Assumption Evaluation: Time to 12 Weeks Confirmed Disability Progression as Measured by at least 1 of 4 Types of Events	ITT Population	Part B
15.39.1	Distribution of 12 Weeks Confirmed Disability Progression as Measured by at least 1 of 4 Types of Events by Treatment Group	ITT Population	Part A
15.39.2	Distribution of 12 Weeks Confirmed Disability Progression as Measured by at least 1 of 4 Types of Events by Treatment Group	ITT Population	Part B
15.40.1	Exploratory Analysis: Time to 24 Weeks Confirmed Disability Progression as Measured by EDSS	ITT Population	Part A
15.40.2	Exploratory Analysis: Time to 24 Weeks Confirmed Disability Progression as Measured by EDSS	ITT Population	Part B
15.41.1	Exploratory Analysis Proportional Hazards Assumption Evaluation: Time to 24 Weeks Confirmed Disability Progression as Measured by EDSS	ITT Population	Part A
15.41.2	Exploratory Analysis Proportional Hazards Assumption Evaluation: Time to 24 Weeks Confirmed Disability Progression as Measured by EDSS	ITT Population	Part B
15.42.1	Distribution of 24 Weeks Confirmed Disability Progression as Measured by EDSS by Treatment Group	ITT Population	Part A
15.42.2	Distribution of 24 Weeks Confirmed Disability Progression as Measured by EDSS by Treatment Group	ITT Population	Part B
15.43	Exploratory Analysis: Number of New T1-Hypointense Lesions at Week 48	mITT1 Population	Part A

Summary number	Title	Population	Data Lock
15.44	Descriptive Statistics for the Number of New T1-Hypointense Lesions at Week 48 by Treatment Group	mITT1 Population	Part A
15.45	Exploratory Analysis: T1-Hypointense Lesion Volume Change From Baseline to Week 48	mITT1 Population	Part A
15.46	Descriptive Statistics for T1-Hypointense Lesion Volume and Change From Baseline to Week 48 by Treatment Group	mITT1 Population	Part A
15.47	Exploratory Analysis: T2 Lesion Volume Change From Baseline to Week 48	mITT1 Population	Part A
15.48	Descriptive Statistics for T2 Lesion and Volume Change From Baseline to Week 48 by Treatment Group	mITT1 Population	Part A
15.49	Exploratory Analysis: Normalized Thalamic Volume Percent Change From Baseline at Week 48	mITT1 Population	Part A
15.50	Descriptive Statistics for Normalized Thalamic Volume Percent Change From Baseline to Week 48 by Treatment group	mITT1 Population	Part A
15.51	Exploratory Analysis: Mean Cortical Thickness Percent Change From Baseline to Week 48	mITT1 Population	Part A
15.52	Descriptive Statistics for Mean Cortical Thickness Percent Change From Baseline to Week 48 by Treatment Group	mITT1 Population	Part A
15.53	Exploratory Analysis: Normalized White Matter Volume Percent Change From Baseline to Week 48	mITT1 Population	Part A
15.54	Descriptive Statistics for Normalized White Matter Volume Percent Change From Baseline to Week 48 by Treatment Group	mITT1 Population	Part A
15.55	Exploratory Analysis: Mean Upper Cervical Cord Area Percent Change From Baseline to Week 48	mITT1 Population	Part A
15.56	Descriptive Statistics for Mean Upper Cervical Cord Area Percent Change From Baseline to Week 48 by Treatment Group	mITT1 Population	Part A
15.57	Exploratory Analysis: Number of T2 Cervical Cord Lesions at Week 48	mITT1 Population	Part A
15.58	Descriptive Statistics for the Number of T2 Cervical Cord Lesions at Week 48 by Treatment Group	mITT1 Population	Part A
15.59	Exploratory Analysis: Mean MTR Normal-Appearing Brain Tissue Percent Change From Baseline to Week 48	mITT1 Population	Part A
15.60	Descriptive Statistics for Mean MTR Normal-Appearing Brain Tissue Percent Change From Baseline to Week 48 by Treatment group	mITT1 Population	Part A
15.61.1	Exploratory Analysis: 9-Hole Peg Test Score Change From Baseline to Week 48	mITT2 Population	Part A
15.61.2	Exploratory Analysis: 9-Hole Peg Test Score Change From Baseline to Each Visit	mITT2 Population	Part B
15.62.1	Descriptive Statistics for 9-Hole Peg Test Score and Change From Baseline to Each Visit by Treatment Group	mITT2 Population	Part A

Summary number	Title	Population	Data Lock
15.62.2	Descriptive Statistics for 9-Hole Peg Test Score and Change From Baseline to Each Visit by Treatment Group	mITT2 Population	Part B
15.63.1	Exploratory Analysis: Symbol Digit Modalities Test Score Change From Baseline to Week 48	mITT2 Population	Part A
15.63.2	Exploratory Analysis: Symbol Digit Modalities Test Score Change From Baseline to Each Visit	mITT2 Population	Part B
15.64.1	Descriptive Statistics for Symbol Digit Modalities Test Score and Change From Baseline to Each Visit by Treatment Group	mITT2 Population	Part A
15.64.2	Descriptive Statistics for Symbol Digit Modalities Test Score and Change From Baseline to Each Visit by Treatment Group	mITT2 Population	Part B
15.65.1	Exploratory Analysis: Low Contrast Visual Acuity Score (Chart Type 100%) Change From Baseline to Week 48	mITT2 Population	Part A
15.65.2	Exploratory Analysis: Low Contrast Visual Acuity Score (Chart Type 100%) Change From Baseline to Each Visit	mITT2 Population	Part B
15.66.1	Descriptive Statistics for Low Contrast Visual Acuity Score (Chart Type 100%) and Change From Baseline to Each Visit by Treatment Group	mITT2 Population	Part A
15.66.2	Descriptive Statistics for Low Contrast Visual Acuity Score (Chart Type 100%) and Change From Baseline to Each Visit by Treatment Group	mITT2 Population	Part B
15.67.1	Exploratory Analysis of Low Contrast Visual Acuity Score (Chart Type 2.5%) Change From Baseline to Week 48	mITT2 Population	Part A
15.67.2	Exploratory Analysis of Low Contrast Visual Acuity Score (Chart Type 2.5%) Change From Baseline to Each Visit	mITT2 Population	Part B
15.68.1	Descriptive Statistics for Low Contrast Visual Acuity Score (Chart Type 2.5%) and Change From Baseline to Each Visit by Treatment Group	mITT2 Population	Part A
15.68.2	Descriptive Statistics for Low Contrast Visual Acuity Score (Chart Type 2.5%) and Change From Baseline to Each Visit by Treatment Group	mITT2 Population	Part B
15.69.1	Exploratory Analysis: Low Contrast Visual Acuity Score (Chart Type 1.25%) Change From Baseline to Week 48	mITT2 Population	Part A
15.69.2	Exploratory Analysis: Low Contrast Visual Acuity Score (Chart Type 1.25%) Change From Baseline to Each Visit	mITT2 Population	Part B
15.70.1	Descriptive Statistics for Low Contrast Visual Acuity Score (Chart Type 1.25%) and Change From Baseline to Each Visit by Treatment Group	mITT2 Population	Part A
